### **7.2.2.2 Corticosteroids**

All subjects who weigh  $\geq 45$  kg should receive 0.5 g IV methylprednisolone on both Day 1 and Day 2 (a total of 1 g), before oral corticosteroid therapy is started on Day 3. All subjects who weigh  $< 45$  kg should receive 0.25 g IV methylprednisolone on both Day 1 and Day 2 (a total of 0.5 g). When subjects are receiving IV methylprednisolone, they should not receive oral corticosteroids on the same day.

If it is considered to be in the subject's best interest, IV methylprednisolone treatment may be started during the screening period, but no more than 1 g in total may be administered for the

screening period and Day 1 and/or Day 2 combined (0.5 g in subjects who weigh <45 kg). Subjects receiving IV methylprednisolone in the 3 months prior to screening must be discussed with the Medical Monitor prior to initiating further IV methylprednisolone. Also, IV corticosteroid therapy to be administered during screening must be discussed with the Medical Monitor in advance. If IV corticosteroid therapy is administered by the site during screening, the dose administered on Day 1 and/or Day 2 will be 1 g minus the dose administered during screening. The maximum daily dose of methylprednisolone administered on Day 1 and/or Day 2 is 0.5 g. See below for examples:

- Example 1: If a 0.6 g dose of IV methylprednisolone is administered during screening, then  $(1 - 0.6) = 0.4$  g IV methylprednisolone will be administered on Day 1, followed by the oral steroid dosing schedule in [Table 1](#), beginning on Day 2 or 3.
- Example 2: If the dose administered during screening is 0.3 g, then the total residual dose required is  $(1 - 0.3) = 0.7$  g. Because 0.7 g is greater than the maximum daily dose allowed, 0.35 g will be administered on Day 1 and 0.35 g on Day 2, followed by the oral steroid dosing schedule in [Table 1](#), beginning on Day 3. If IV methylprednisolone therapy is administered in the 2 weeks prior to the start of screening then the subject is excluded from the study (see Section 7.8.1, [Prohibited Medications](#)), unless approved by the Medical Monitor.
- Example 3: In a 40 kg subject, if a 0.3 g dose of IV methylprednisolone is administered during screening then  $(0.5 - 0.3) = 0.2$  g IV methylprednisolone will be administered on Day 1, followed by the oral steroid dosing schedule in [Table 1](#), beginning on Day 2 or 3.

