If at screening the Investigator determines a subject requires IV corticosteroid therapy, every effort should be made to collect both morning urine specimens (for UPCR determination) before initiation of the IV steroids. If this cannot be done, the Medical Monitor should be contacted in advance of the therapy (see Section 9.2.1, [Screening Visit Procedures](#)).

In the case of the full 1 g IV methylprednisolone being administered prior to randomization (or 0.5 g in a subject <45 kg), it is acceptable for oral prednisone as per dosing schedule to be administered on Day 1.

The starting dose of oral prednisone will be 20 mg/day for subjects <45 kg and 25 mg/day for subjects  $\geq 45$  kg. The dose will be reduced according to the tapering schedule below, see [Table 1](#). Refer to [Appendix 4](#) for a conversion table of various formulations of steroids.

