### **9.2.1 Screening Visit Procedures**

The screening visit (Visit 1) will take place within 30 days prior to Visit 2/baseline (Day 1). Screening will include provision of informed consent, physical examination including weight, and height, medical history (including SLE and LN history), vital signs measurements, 12-lead ECG, and review of prior and concomitant medications and entry criteria. Any AEs which occur after informed consent will be recorded. Urine samples will be collected for urinalysis and urine microscopy; first morning void urine samples (for determination of UPCR) will be collected on 2 days during the screening period and must be returned and the results evaluated prior to Visit 2. An average of the 2 screening UPCRs will be used as a marker of baseline urine protein excretion. Baseline proteinuria level is determined by a mean of 2 first morning void urine samples taken during the screening period. The lowest of pre-dose eGFR assessments will be used as the marker of baseline renal function. It is recommended that in the event that IV corticosteroids are administered during screening, the 2 first morning urine voids are to be collected prior to administration of the corticosteroids (see Section 7.2.2.2, [Corticosteroids](#)). In the case where this is not possible, then the marker of baseline urine protein excretion will be based upon the Visit 1 UPCR collection only. This must be discussed with the Medical Monitor prior to enrollment. Please note that the results of the 24-hour urine collection will have to be available prior to the Baseline Visit.

Blood samples will be drawn according to [Table 2](#).

If the subject is from an area where TB is endemic or whose history suggests an increased personal risk, e.g., from contact with people with TB or travel to areas with endemic TB, the subject will be carefully evaluated for latent or active TB.

Women of childbearing potential should have a negative serum pregnancy test result before randomization. Study treatment cannot be initiated by the physician until a report of a serum negative pregnancy test has been obtained.

If a subject has not met the requirements in Inclusion Criteria #4 due to not having kidney biopsy result within the required time frame, a kidney biopsy can be performed as per local procedures, after signing the study consent, provided the results can be obtained and reviewed prior to randomization.

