- 3 Subjects who do not enroll into the continuation study will have a follow up safety visit 4 weeks after the last dose of study treatment.
- 4 If a subject has not had a recent kidney biopsy, one may be performed to assess eligibility for the study provided informed consent has been given and results are received prior to randomization. If one is performed as part of standard of care after randomization, the results will be recorded in the electronic case report form.
- 5 Complete physical examination at screening, abbreviated examination at all other applicable visits. Height is measured at screening only.
- 6 During the study, and after screening, in the event that a subject is noted to have a QTcF value exceeding 500 msec, or >60 msec more than baseline, the ECG will be repeated. Electrocardiograms will be recorded digitally after the subject has been in a resting, supine position for at least 5 minutes.
- 7 Week 12 only.
- 8 Laboratory assessments will be performed according to the schedule in Section 6.13.2; subjects must be fasting for at least 8 to 12 hours at baseline and end of study/early termination.
- 9 Blood samples will be collected at 0 and 2 hours post dose on subjects who provide consent for pharmacokinetics.
- 10 Two FMV specimens, to be performed and resulted before baseline.
- 11 24-hour urine collection should begin 2 days prior to the scheduled study visit in order not to coincide with the FMV sampling due on the day of the study visit.
- 12 Serum pregnancy test to be evaluated at central laboratory at screening, Week 24, and Week 52; urine pregnancy test will be performed locally at all other applicable visits.
- 13 Concomitant medications include all herbal medicines and supplements taken by the subject.
- 14 For details on HRQoL assessments, see Section 6.11.4.8.
- 15 For details on Healthcare Resource Utilization, see Section 6.11.4.11.
- 16 Compliance only.
- 17 All scheduled procedures must be done prior to first dose, including IV methylprednisolone and MMF.
- 18 For subjects not on MMF during screening, will start receiving MMF therapy at the Baseline Visit and return for local complete blood count assessments at Weeks 1 and 3 after randomization.
- 19 IV methylprednisolone administered 0.5 g on baseline and Day 2. If IV corticosteroids must be administered during screening then the FMV urine specimens will be collected prior to the infusion.

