#### **6.2.2 Baseline**

Except for parameters detailed later in this section, baseline is defined as the last non-missing value (either scheduled, unscheduled or repeat) before the subject receives the first dose of study drug on Day 1. As assessments on day 1 are scheduled to be undertaken prior to taking study drug, day 1 assessments can be defined as baseline.

eGFR baseline will be calculated as the lowest measurement available prior to dosing.

Urine creatinine baseline will be calculated as the mean of the latest 2 pre-randomization values. Should only 1 value be available it will be used as the baseline value.

Urine protein baseline will be calculated as the mean of the latest 2 pre-randomization values. Should only 1 value be available it will be used as the baseline value.

UPCR values are calculated by the laboratory as the ratio of urine protein to creatinine. The ratio is only calculated where laboratory tests produce a result for both the creatinine and the protein. UPCR baseline will be calculated as the mean of the latest 2 pre-randomization values. Should only 1 value be available it will be used as the baseline value.

For the endpoints of change from baseline in UPCR and also for partial response endpoints (that incorporate a 50% reduction from baseline in UPCR), a second definition of baseline (alternative baseline) UPCR will be defined as the lowest measurement available prior to dosing.

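### SAP 6.2.2 has no exception for a urine sample taken after screening IV steroids, whereas Protocol 9.2.1 then bases baseline proteinuria on Visit 1 alone

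*SAP*

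**What the plan says.** **Protocol.** The general rule in Section 9.2.1 is a two-sample mean: "An average of the 2 screening UPCRs will be used as a marker of baseline urine protein excretion". Section 7.2.2.2 allows steroids before randomization: "IV methylprednisolone treatment may be started during the screening period". It treats collecting both samples first as a best effort: "every effort should be made to collect both morning urine specimens (for UPCR determination) before initiation of the IV steroids". If that cannot be done, the Medical Monitor is to be contacted. Section 9.2.1 then says which baseline applies: "then the marker of baseline urine protein excretion will be based upon the Visit 1 UPCR collection only".

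**SAP.** Section 6.2.2 gives one rule for every subject: "UPCR baseline will be calculated as the mean of the latest 2 pre-randomization values". The only fallback is "Should only 1 value be available it will be used as the baseline value". Urine protein baseline is worded the same way. For supplementary analyses, "a second definition of baseline (alternative baseline) UPCR will be defined as the lowest measurement available prior to dosing". A footnote to the schedule in Table 1.1 says "If IV corticosteroids must be administered during screening then the FMV urine specimens will be collected prior to the infusion", but gives no rule for the case where this does not happen. Section 9, which lists changes from the protocol's planned analysis, does not mention the UPCR baseline.

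**The concern.** A void collected after the infusion and reported by the laboratory is an available value. Under SAP 6.2.2 as printed it is averaged into baseline; under Protocol 9.2.1 it is not. Two programmers, each following one document, would derive different baselines for the same subject.

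The planned IV methylprednisolone falls on Days 1 and 2, so for most subjects baseline UPCR precedes the pulse. In the affected subgroup the SAP baseline would lie partly after it, and a reduction from baseline would mean something different there.

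Baseline UPCR is used in:
- partial renal response at Weeks 24 and 52 and time to 50% reduction (SAP 6.11.3.2 and 6.11.3.3), which are three of the five hypotheses in the Hochberg family (SAP 6.11.5.2);
- change from baseline in UPCR (SAP 6.11.4.3);
- the primary logistic model, as a covariate (SAP 6.11.2.1).

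**Working it through.** The plan gives no figure for this point. Its sample size (162 per arm, 20.0% versus 34.4%) does not use baseline UPCR and is unaffected. The continuity-corrected formula gives 163 per arm, which agrees with the stated 162 to within rounding.

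**Inputs**
- V1: the Visit 1 UPCR, taken to precede the infusion.
- r: the fraction by which the later void lies below V1. The documents give no value and no time course. Protocol 1.1.1 supports only the direction, by describing pulse steroids as a rapid treatment for relapse. A range of 10-40% is assumed.

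**Baseline under each document**
- Protocol 9.2.1: B = V1
- SAP 6.2.2: B = [V1 + V1(1 - r)] / 2 = V1(1 - r/2)

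**Fall from V1 needed to count as a 50% reduction**
- Protocol: 50%
- SAP: 1 - 0.5(1 - r/2) = 0.5 + r/4

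| Assumed r | SAP baseline / V1 | 50% target / V1 | Fall from V1 needed |
|---|---|---|---|
| 10% | 0.95 | 0.475 | 52.5% |
| 20% | 0.90 | 0.450 | 55.0% |
| 30% | 0.85 | 0.425 | 57.5% |
| 40% | 0.80 | 0.400 | 60.0% |

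Example: with V1 = 3.0 mg/mg and r = 30%, the SAP baseline is 2.55 against 3.0, and the 50% target is 1.275 against 1.5 mg/mg.

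The direction depends on the data. If the later void were 20% higher than Visit 1 (r = -20%), the SAP baseline would be 10% higher and a 45% fall would be enough.

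**Does the alternative baseline restore the protocol rule?** No. The lowest pre-dose value in this two-sample case is V1(1 - r) when r is positive. That is r below V1, twice the r/2 shift under the main definition.

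**The case against.** **The SAP's premise.** SAP 6.2.2 does not mention steroids. The footnote to its schedule, like the one in the protocol, has the voids collected before the infusion. Where that happens both values are pre-steroid and the two rules agree. Where no second void exists, the single-value fallback also agrees, provided that the one value is from Visit 1. A reader might infer that the SAP deliberately chose to average post-steroid samples; the text supports only that it has no exception. What remains is the case of a second void collected after the infusion, which Protocol 7.2.2.2 and 9.2.1 both foresee.

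**The protocol's own general wording.** The Synopsis and Section 4.1 give the two-value mean without qualification, and the SAP follows them. That explains the SAP wording, but the specific exception in 9.2.1 still qualifies the general rule.

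**Unseen text.** SAP 6.2.14 (FMV and 24-Hour Urine) is in the table of contents, but its text was not in the copy reviewed. A rule there cannot be excluded; 6.2.2 does not refer to one.

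**Size across the trial.** Screening steroids need prior discussion with the Medical Monitor, so the subgroup is probably small. As an illustration only, assume a log-scale SD of 0.8 and a 50% chance of partial response under the protocol baseline. That chance becomes Φ(ln 0.95 / 0.8) = 47.4% at r = 10% and Φ(ln 0.80 / 0.8) = 39.0% at r = 40%, drops of 2.6 and 11.0 points. If 5% to 20% of subjects were affected, the overall rate would fall by 0.05 × 2.6 = 0.1 to 0.20 × 11.0 = 2.2 points. None of these inputs is in the documents. This objection stands as a limit on importance.

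**Supplementary analyses.** Repeating the endpoints with the lowest pre-dose value shows how they respond to a larger shift in the same direction. It does not give the result under the protocol's baseline.

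**Conclusion.** The inconsistency holds on the printed text: for subjects whose second void follows screening IV steroids, the SAP and the protocol define different baselines, and SAP Section 9 does not list the departure. Subject to SAP 6.2.14, this needs a clarification; it is not a threat to the trial's conclusion.

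For an affected subject the SAP baseline is 5-20% below the protocol baseline if r is 10-40%. That range is an assumption, and the number of affected subjects is unknown.

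Two stronger readings are tempting, and the documents support neither:
- **Bias in favor of one arm.** The values are obtained before randomization, so no systematic difference between arms is expected. A lower baseline makes a 50% reduction harder to reach in both arms; the cost is some misclassification and lost precision.
- **Damage to the primary result.** The primary UPCR criterion is an absolute 0.5 mg/mg. Baseline UPCR enters that analysis only as a covariate.

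**What to change.** Add one sentence to SAP 6.2.2: for subjects given IV corticosteroids in screening before the second void was collected, baseline UPCR and urine protein use the Visit 1 value only, per Protocol 9.2.1. If the sponsor prefers the unconditional mean, record and justify the departure in SAP Section 9. If SAP 6.2.14 already has such a rule, a cross-reference from 6.2.2 is enough.

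Flag affected subjects while blinded, by comparing steroid dates with central-laboratory sample dates; same-day cases may need collection times. Report the number flagged by arm.

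The cost is one sentence, one derived flag and one line in a table. Protocol 7.5.3 and 7.8 already require the steroid records in the eCRF. Design, sample size and treatment do not change.

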### **6.2.3 Early Terminations Assessments**

Data collected at Early Termination (ET) assessments will be mapped to the visits closest to the date of termination.

### **6.2.4 Duration/Study Day/Time**

Study day will be calculated as the number of days from first dose of study drug (Day 1).

- Date of event – date of first dose of study drug + 1, for events on or after first dose
- Date of event – date of first dose of study drug, for events before first dose
- To this end, Day 0 remains undefined.

For all time to event analyses, subjects not reporting the specified endpoint will be censored at the time that the subjects were last known not to have experienced the endpoint. For all endpoints not encompassing death, all deaths will be treated as censoring events. In complex cases where the censoring time of the subject is uncertain, the case will be reviewed by the [REDACTED] statistician and a censoring time will be assigned and programmed prior to database lock.

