Baseline assessments will be performed before the first dose of study treatment is administered on Day 1. Using an interactive web response system (IWRS), eligible subjects will be randomized to receive either oral voclosporin 23.7 mg twice daily (BID) or matching placebo for 52 weeks. All subjects who weigh  $\geq 45$  kg should receive 0.5 g IV methylprednisolone on both Day 1 and Day 2 (a total of 1 g), before oral corticosteroid therapy is started on Day 3. All subjects who weigh  $< 45$  kg should receive 0.25 g IV methylprednisolone on both Day 1 and Day 2 (a total of 0.5 g). When subjects are receiving IV methylprednisolone, they should not receive oral corticosteroids on the same day. Starting at the Baseline Visit, all subjects will also receive background therapy with mycophenolate mofetil (MMF).

All subjects will return for assessment of efficacy and safety at Day 2 and Weeks 2, 4, 8, 12, 16, 20, 24, 30, 36, 42, 48, and 52. In addition, subjects not on MMF during screening, will start receiving MMF at the Baseline Visit and will return for local complete blood count assessments at Weeks 1 and 3 after randomization.

All subjects, completed or withdrawn, will complete the End of Treatment/Early Termination assessments (Visit 15) at Week 52 or at the time of early termination. Subjects who do not enroll in the planned continuation study will attend the Safety Follow-up Visit (Visit 16) at Week 56 to collect any new AEs and concomitant medications. At the follow-up visit, urine protein creatinine ration (UPCR) and estimated glomerular filtration rate (eGFR) will be assessed as well.

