### 3 ENDPOINTS

#### 3.1 Primary Endpoint

Renal response at Week 52 will be adjudicated by the Clinical Endpoints Committee (CEC) based on the following parameters:

- UPCR of  $\leq 0.5$  mg/mg, and
- eGFR  $\geq 60$  mL/min/1.73 m^2 or no confirmed decrease from baseline in eGFR of  $>20\%$ , and
- Received no rescue medication for LN (see Protocol Section 7.8, Prohibited Therapy and Concomitant Treatment), and
- Did not receive more than 10 mg prednisone for  $\geq 3$  consecutive days or for  $\geq 7$  days in total during Weeks 44 through 52, just prior to the renal response assessment

The CEC will also take into account the following:

- Subjects who withdraw from the study prior to the Week 52 assessment and provide insufficient week 52 data to determine response will be defined as non-responders. Subjects who discontinue study drug but continue to attend study visits (as is the expectation) will have their data assessed for response.
- eGFR values eliminating a subject from complete remission should be accompanied by a treatment or disease-related treatment-emergent adverse event (TEAE) that impacts eGFR. Full details are given in Section [6.11.1](#).
- The CEC is independent and blinded from the treatment groups.

The primary endpoint estimand is the proportion of subjects showing renal response as adjudicated by the CEC in the ITT population when comparing voclosporin and placebo at Week 52. It is assessed in all randomized subjects who were recruited according to the inclusion/exclusion criteria of the protocol.

The variable is binary and indicates a response if a subject shows, at 1 year, adequate UPCR with no signs of detrimental impact on eGFR. Subjects who cannot be shown to be responders through their 1 year data (or absence thereof) are defined as non-responders.

Intercurrent events include:

- Treatment discontinuation for any reason
  - the subject remains on study, allowing the primary endpoint to be assessed at 1 year.
- Study discontinuation
  - resulting in insufficient information at 1 year to ascertain response status leading to assumed non-response.
- Rescue medication taken at any time prior to the primary assessment at 1 year
  - results in non-response. Rescue medication is adjudicated by the Clinical Endpoints Committee.
- Death at any time prior to the 1 year primary assessment
  - results in assumed non-response.

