## 4 SAMPLE SIZE

The total sample size will be approximately 324 subjects (162 subjects per treatment arm). This is based on the following assumptions:

- A two group continuity corrected Chi square test with a 0.05 two-sided significance level will have 80% power to detect the difference between a placebo response rate of 20.0% and a voclosporin response rate of 34.4% (odds ratio=2.1) when the sample size in each group is 162 (total N=324).
- The effect of withdrawals will be investigated. Subjects withdrawing for any reason will be counted as non-responders in the primary analysis and therefore no adjustment of sample size for withdrawals is necessary.
- The impact of withdrawals on primary endpoint will be investigated in the tipping point analysis.

Table 4.1 shows the voclosporin response rates required to maintain a minimum 80% power at the planned sample size for given placebo response rates. These response rates all lead to odds ratios of around 2, which is a clinically relevant effect.

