## **5 RANDOMIZATION**

All subjects enrolled must be identifiable throughout the study. The Investigator will maintain a list of subject numbers and subject names to enable records to be found at a later date. Subjects will be allocated a subject number at the screening visit and registered with an interactive central randomization system. Subjects meeting the required eligibility criteria will be randomized to treatment at Visit 2 (baseline).

The randomization will be stratified by biopsy class (Class V only versus Others) and by prior MMF use at time of screening. The subjects will be randomized in a ratio of 1:1 to receive either voclosporin 23.7 mg BID or matching placebo. To help ensure balance, a centralized randomization will be utilized where region will be employed as a blocking factor. This will ensure balance between treatment groups within each of the 4 regions: North America, Latin America, Europe / South Africa and Asia Pacific.

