#### 6.11.3.1 Time (weeks) to UPCR of $\leq 0.5$ mg/mg

Time to UPCR of  $\leq 0.5$  mg/mg will be analyzed by comparing the survivor function between treatment arms. It will be estimated using Kaplan-Meier methodology and will be presented as a plot showing a line for each treatment group as well as the numbers remaining at risk for each treatment group at different time points. Median time to UPCR of  $\leq 0.5$  mg/mg along with two-sided confidence intervals will be displayed. Time to event will be measured as the number of weeks from day of randomization to the day of the event. Subjects who do not experience an event will be censored on the day of their last assessment of UPCR.

A Cox's proportional hazards model will be fitted to assess the significance of the differences between treatment arms. The model will include terms for treatment arm, baseline UPCR, biopsy class, MMF use at baseline and region. Estimates of the treatment effects will be expressed as hazard ratios (and associated 95% CI) for voclosporin relative to placebo. Hazard ratios greater than unity will indicate the hazard to be greater for voclosporin than for placebo and therefore indicate that the events in question generally occur earlier on active voclosporin and, for this endpoint, a benefit of voclosporin (Table 14.2.2). The log-log survivor function to proportional hazards will be assessed. A listing of time (weeks) to UPCR of  $\leq 0.5$  mg/mg responders and censors will be provided.

#### 6.11.3.2 Partial renal response as defined by 50% reduction from baseline UPCR at Weeks 24 and 52

Change from baseline in UPCR will be calculated as the post baseline measurement minus the baseline measurement. Percent change from baseline will be calculated as:

- Percent change from baseline (UPCRpc) =  $\left( \frac{\text{Change from baseline}}{\text{Baseline}} \right) \times 100$

A 50% reduction in UPCR will be indicated by UPCRpc  $\leq -50$ . Subjects with missing UPCRpc values will be considered non-responders. This endpoint will be analyzed and presented similarly to the primary efficacy endpoint as described in Section 6.11.2 (Table 14.2.3). A listing of subjects considered responders will be provided.

A supplementary analysis of partial response at both Week 24 and Week 52 will be undertaken using the alternative baseline definition (Section 6.2.2) of the lowest UPCR value pre-dosing.

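### Censoring deaths in the two time-to-response key secondary endpoints makes the Kaplan-Meier response curves and quantiles too favourable, more so in the arm with more deaths

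*SAP*

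**What the plan says.** SAP 6.2.4 gives the general rule: "For all endpoints not encompassing death, all deaths will be treated as censoring events". SAP 6.11.3.1, on time to UPCR ≤0.5 mg/mg, adds: "Subjects who do not experience an event will be censored on the day of their last assessment of UPCR". It makes no exception for subjects who die. SAP 6.11.3.3 carries the same method over to time to 50% UPCR reduction. Neither event definition includes death.

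For both endpoints SAP 6.11.3 asks for Kaplan-Meier plots, the 25th, 50th and 75th quantiles with confidence intervals, and a Cox hazard ratio with its p-value. SAP 6.11.5.2 places both in the Hochberg family, with three binary endpoints. No cumulative incidence or competing-risk analysis is planned, and no sensitivity analysis addresses death. The one supplementary analysis, for time to 50% reduction, changes only the UPCR baseline.

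Elsewhere death or missing data counts as failure. SAP 3.1 lists "Death at any time prior to the 1 year primary assessment" among the intercurrent events and assigns it non-response. SAP 6.11.3.2 counts a missing UPCR change as non-response in the partial-response endpoints.

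**The concern.** Both events are favourable. Kaplan-Meier treats a censored subject as someone who would have gone on to respond at the same rate as those still followed. That is reasonable for a subject who is merely unobserved, but a dead subject cannot respond. The complement of the curve then estimates response in a hypothetical trial without deaths, while a reader will take it as the proportion of randomized subjects who responded by a given week.

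The overstatement grows with the number of deaths, so unequal mortality produces a gap between arms that is not a treatment benefit. The possibility is foreseeable: Protocol 1.2.4.2 reports 10 Phase 2 deaths at the dose used here, 2 at the higher dose and 1 on placebo. At stake are the curves and quantiles for two multiplicity-controlled endpoints, and what the accompanying hazard ratio is taken to mean.

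**Working it through.** **The plan's own figure.** SAP 4 assumes 20.0% response on placebo and 34.4% on voclosporin, and arrives at 162 per arm. On the test it says: "A two group continuity corrected Chi square test with a 0.05 two-sided significance level will have 80% power". The usual formula gives 148.7 per arm without the continuity correction and 162.3 with it, so 162 is reproduced to within rounding. The odds ratio is (0.344/0.656)/(0.20/0.80) = 2.10. The documents give no event rate, hazard ratio or power for the time-to-response endpoints, so nothing of theirs can be reproduced there.

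**Inputs.**
- From the documents: 162 per arm, 1:1 allocation, 52 weeks of treatment.
- Phase 2 deaths: 10 (low dose) and 1 (placebo), from Protocol 1.2.4.2.
- Phase 2 arm sizes: Protocol 1.2.5 gives 6 low-dose subjects as 6.7%, hence 89 or 90; 89 is used, and 88 is assumed for placebo. Death risks are 10/89 = 11.2% and 1/88 = 1.1%, or about 18 and 2 deaths per 162.
- Assumptions: constant hazards, 40% to 80% response by Week 52, and every Phase 3 death rate.

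**Formulas.** Let h be the weekly response hazard and m the weekly death hazard.
- Kaplan-Meier, deaths censored: 1 − exp(−52h).
- Cumulative incidence, death competing: [h/(h+m)] × [1 − exp(−52(h+m))].

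**Example, 60% response on Kaplan-Meier, voclosporin.** h = −ln(0.40)/52 = 0.01762 and m = −ln(1 − 10/89)/52 = 0.00229. Cumulative incidence = (0.01762/0.01991) × (1 − 0.3551) = 0.8849 × 0.6449 = 57.1%. For placebo, m = 0.00022 and the result is 59.7%.

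| Deaths, v / p | 1−KM, v / p | Cumulative incidence, v / p | Excess in v−p difference, points |
|---|---|---|---|
| 11.2% / 1.1% | 40 / 40 | 37.9 / 39.8 | 1.9 |
| 11.2% / 1.1% | 60 / 60 | 57.1 / 59.7 | 2.6 |
| 11.2% / 1.1% | 80 / 80 | 76.6 / 79.7 | 3.1 |
| 11.2% / 1.1% | 60 / 45 | 57.1 / 44.8 | 2.7 |
| 5% / 1% | 60 / 60 | 58.7 / 59.7 | 1.0 |
| 2% / 1% | 60 / 60 | 59.5 / 59.7 | 0.3 |
| 2% / 2% | 60 / 60 | 59.5 / 59.5 | 0.0 |

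(v = voclosporin, p = placebo; excess computed before rounding.) Over 40% to 80% response the excess is 0.7 to 1.2 points at 5% against 1% deaths, and 0.2 to 0.3 at 2% against 1%.

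**Quantiles at 60% response.** The Kaplan-Meier median is ln(2)/h = 39.3 weeks in both arms. The cumulative-incidence median is −ln(1 − 0.5(h+m)/h)/(h+m) = 41.8 weeks on voclosporin and 39.6 on placebo, a gap of about 2 weeks that Kaplan-Meier hides. The voclosporin 25th percentile moves only from 16.3 to 16.7 weeks. At 3% deaths the median moves 0.6 weeks.

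**Cox model.** This was simulated with 600 runs per scenario, 162 per arm, the scheduled visits and an unadjusted model, with no true difference between arms.
- Death unrelated to response prospects, Phase 2 death rates: the hazard ratio is 0.99 to 1.00 with deaths censored, and 0.92 to 0.94 with the dead kept at risk.
- All deaths among subjects who would not have responded (a deliberate extreme), Phase 2 rates: the hazard ratio with deaths censored is 1.10 at 60% response and 1.13 at 80%. False significance favouring voclosporin is 9.5% and 15.8%, against a nominal 2.5%.
- The same extreme with 5% against 1% deaths: hazard ratio 1.03 to 1.05, false significance 3.2% to 5.2%. The Monte Carlo standard error near 2.5% is √(0.025 × 0.975/600) = 0.6 points, so 3.2% is not clearly above nominal.

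**The case against.** The strongest reply is that the formal decision does not use the Kaplan-Meier curve. Hochberg takes the Cox p-value, and a Cox model with deaths censored is a legitimate cause-specific comparison. This stands. A reader might infer that the death rule inflates the type 1 error of the Hochberg family. The documents do not support that: they give no reason to expect deaths to fall only among poor responders, and the simulated inflation needs that extreme together with a large death imbalance.

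A reader might also infer that these endpoints contradict the primary estimand. SAP 3.1 defines that estimand for the primary endpoint only. The time-to-event tests ask whether events come sooner, which is a different question, and both partial-response tests in the same family already count missing UPCR as failure. The difference in handling deserves a stated reason, but it is not a contradiction.

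The Phase 2 imbalance may not recur. The higher dose had 2 deaths, and 11 of the 13 deaths were in Asia. The documents give no Phase 3 death rates. Finally, making an analysis with the dead kept at risk the main test would swap one estimand for another: its hazard ratio falls below 1 through mortality alone. That is a good reason to leave the planned test in place.

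What remains is the display. No argument above makes 1 minus Kaplan-Meier a correct estimate of the proportion responding when subjects die, and no planned analysis of these two endpoints shows the correct one.

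**Conclusion.** The point holds for the curves and quantiles. The direction is certain whenever subjects die without responding; the difference between arms depends on a death imbalance that the documents do not give. Under constant hazards and 40% to 80% response, it is about 2 to 3 points at Phase 2 death rates, about 1 point at 5% against 1%, and near nil when deaths are few or balanced.

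The Cox comparison stands as a cause-specific hazard ratio if death is unrelated to response prospects. It does not describe the chance of responding, and it can favour the arm with more deaths if those who die were unlikely to respond. The primary analysis is unaffected. This is an inexpensive improvement, and not a defect that undermines the planned tests.

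**What to change.** 1. Keep the planned Cox model as the Hochberg test for both endpoints, and state in SAP 6.11.3 that its hazard ratio is cause-specific.
2. In SAP 6.11.3, 6.11.3.1 and 6.11.3.3, replace the Kaplan-Meier curves and quantiles with cumulative incidence treating death as a competing event, or add it alongside. Take the 25th, 50th and 75th quantiles and their intervals from it, reporting a quantile as not reached where that applies.
3. Prespecify one sensitivity analysis per endpoint in which subjects who die without the event remain in the risk set as non-responders until after the last possible Week 52 visit, meaning the end of the ±10-day window. Stopping at the nominal Week 52 day would drop the dead from the risk set before late-window events are counted.
4. Record the departure from Protocol 13.8.3.2, which specifies Kaplan-Meier estimates and medians, in SAP Section 9.

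The cost is one more figure and one more model per endpoint, from data already collected. The sensitivity hazard ratio mixes mortality with proteinuria response and should be labelled so. Subjects lost to follow-up for other reasons remain censored, so these endpoints will still not match every intercurrent-event rule in SAP 3.1.
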